8 OBSERVATIONAL PLAN

8.1 Overall Study Design and Plan – Description

This is a single-center, observational case control study in Italy that follows the use of treatment siltuximab in patients diagnosed with COVID-19 infection who have developed serious respiratory complications. Retrospective data collection will be carried out on patients who have received the drug through the compassionate use program. (this program is still ongoing, and enrolling patients).

Patients receiving siltuximab will be included into this observational study and will be divided into 2 cohorts, split in an approximate 3:1 ratio: 75% will be in Cohort A and are not in an ICU setting and are not on mechanical ventilation, while 25% will form Cohort B and consists of patients in an ICU setting who are receiving invasive ventilation.

[figure not shown]
Each patient will be matched to a consented case control receiving treatment other than siltuximab for their condition.

Match Criteria

Patients receiving siltuximab and controls will be matched according to the following criteria:

- Age (by decades)
- Sex (M/F)
- P/F fraction (<100, 100-150 or >150) at baseline
- Antiviral therapy

Figure 1: Study Design

Procedures outlined in this protocol are based on the compassionate use program, where patients are managed as per clinicians' best judgement and best practice. No procedures are required by this observational protocol. Data on the procedures already performed during the routine diagnosis and treatment of COVID-19 patients will be collected. The list of clinical and laboratory parameters is provided to direct data collection for this observational study (as available in the medical records).

During their hospitalization, patients will be monitored as per standard hospital practice or as per national (emergency) guidelines in accordance with extraordinary circumstances relating to the COVID-19 outbreak. After discharge, patients will be asked to provide (from their primary health care providers) relevant laboratory results for 30 days following start of COVID-19 treatment via ventilation (either mechanical or non-invasive).

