9 STUDY POPULATIONS

9.1 Eligibility

9.1.1 Inclusion Criteria

Patients must meet the following criteria to be eligible to participate in the study:

- 1. Clinical and radiological diagnosis of pulmonary infection by COVID-19
- 2. Positive microbiological evidence of SARS-CoV-2 infection
- 3. Diagnosis of acute respiratory distress syndrome clinical panel in accordance with Berlin 2012 criteria
- 4. For Cohort A only: subjects are eligible if they are enrolled and treated within 48 hours from the beginning of NIV or CPAP
- 5. For Cohort B only: subjects are eligible if they are enrolled and treated within 48 hours from the beginning of invasive ventilation

While approving this protocol, it is understood that the RA/IEC have approved collection and analysis of the data from deceased patients with COVID-19. See also protocol section 10.1.2.

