10.1.1 Tabulated Overview

All available data will be captured from medical records. The following data will be recorded (if available):

Laboratory-confirmed COVID-19 (Positive, validated RT-PCR Assay of nasopharyngeal swabs and ideally serum)

Demographics
Prior medications used

Past Medical History

The following data will be recorded from the time of first ventilation for 30 days (if available):

General Information	
Hospital admission	
ICU admission	
Mobility	
Respiratory parameters	
Use of inotropic medication	
RR/MAP	
Rx (X-Thorax, CT scans)	
Fever/rash/abnormal cardiac function	
Mechanical ventilation	
ECMO	
Infectious Disease Parameters	
Inflammatory markers	
Peripheral edema	
Cytokine panel- Full Cytokine panel workup pre and post treatment (Serum)	
Pre-treatment CRP Levels	
Post-treatment CRP Levels /24h	
Cardiac parameters/Oxygen saturation	
General Disease Parameters	
APACHE II score	
Performance status (ECOG/Karnofsky)	

Laboratory Assessments

Virus titer

IL-6 status Pre-treatment Serum IL-6 levels (ELISA or similar approach, e.g.: Multiplex cytokine array)

Extended blood panel (Hb/Ht), thrombocytes, including PMBC

Coagulation status

History of HIV/HHV-8/Hepatitis/Tuberculosis infections

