10.1.2 Enrollment/Initial Visit

Once a potential patient is identified for inclusion in the observational case control study, the physician will inform the patient about the study. This will include discussing the consent form and asking the patient, if possible, to read and provide consent. Where patient is able to provide only verbal consent (e.g. due to technical reasons, isolation) this consenting will be documented by the doctor who will complete the appropriate paperwork. When the patient is not able to provide consent due to their medical condition, consent for data collection / analysis will given by the doctor.

As COVID-19 is a highly contagious and easily transmissible virus, written consent may not be able to be sought from patients at enrollment. In the interests of human safety, in such circumstances only physicians will sign the informed consent, documenting in the doctor's emergency consent form also the circumstances under which consent was obtained.

Retrospective signed informed consent will be sought from patients when they are clear of the virus and no longer considered to have the potential to transmit COVID-19.

Once at least the doctors emergency consent form is available / there is basis for starting patient data collection and analysis, the physician or a delegate will use a CRF to document the patient's data. Data collection, regardless of type of contact, will follow a standard format and will be conducted equally for all patients.

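### Controls have no index time aligned to their partner's infusion, so failures before infusion cannot be siltuximab events in that cohort but can be control events

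*Protocol*

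**What the plan says.** - **Siltuximab group.** Protocol section 8.1: "Retrospective data collection will be carried out on patients who have received the drug through the compassionate use program". Membership depends on an infusion having been given.
- **Treatment window.** Section 9.1.1, criterion 4 (Cohort A): "subjects are eligible if they are enrolled and treated within 48 hours from the beginning of NIV or CPAP". Criterion 5 (Cohort B): "subjects are eligible if they are enrolled and treated within 48 hours from the beginning of invasive ventilation".
- **State of Cohort A.** Section 8.1: "75% will be in Cohort A and are not in an ICU setting and are not on mechanical ventilation".
- **Observation window.** Section 10.1.1, and the Synopsis in like terms: "The following data will be recorded from the time of first ventilation for 30 days (if available". Section 10.1.2 adds that data collection "will follow a standard format and will be conducted equally for all patients".
- **Controls.** Section 8.1: "Each patient will be matched to a consented case control receiving treatment other than siltuximab for their condition". The match criteria (Synopsis and 8.1) are age by decade, sex, P/F class at baseline and antiviral therapy.
- **Primary endpoints.** Section 6 names invasive ventilation or 30-day death for Cohort A, and ICU stay or 30-day death for Cohort B.
- **Use of the controls.** Section 8.2 includes them so that the groups can be compared directly. Section 11 plans a descriptive comparison within each cohort, and 11.2.3 rules out statistical comparisons.

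**The concern.** The clock starts at first ventilation, but a patient joins the siltuximab group only on reaching an infusion that may come up to two days later. Such a patient is known to have been alive, and in Cohort A not intubated, for that whole interval. Nothing gives the matched control the same guarantee. A patient who is intubated or dies before any infusion is still one who received other treatment, and so is available as a control.

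At stake is the event part of both primary endpoints. A lower siltuximab rate could come from timing alone, in a study whose controls are there to support direct comparison and whose section 11.2.5 foresees early release of results.

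**Working it through.** **Is there an aligning rule?** Taking the passages together:

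1. Group membership is fixed at infusion, 0 to 48 hours after the start of support (8.1 and 9.1.1).
2. The data window starts at first ventilation, with the same collection for all (Synopsis, 10.1.1 and 10.1.2).
3. None of the four match criteria concerns time since ventilation started, or being event-free at a given time.
4. Early deaths are not barred as controls, because 9.1.1 provides for data from deceased patients.

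No rule aligns the two groups.

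**Which events are affected?** Only failures before infusion. A patient infused at 6 hours and intubated at 20 hours is a siltuximab event. A patient intubated before infusion and infused within 48 hours of intubation can enter siltuximab Cohort B, so that failure leaves Cohort A instead of counting there.

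**Size with no drug effect.** The protocol has no power calculation to reproduce. Its split is consistent: 50 × 0.5 = 25 per group, then 25 × 0.75 = 18.75 (about 19) in Cohort A and 25 × 0.25 = 6.25 (about 6) in Cohort B.

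The protocol gives none of these inputs, so they are assumptions:

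- p, the 30-day failure risk from ventilation start: 0.30 to 0.60
- f, the share of those failures in the first 48 hours, spread evenly: 0.10 to 0.40
- T, the hours from ventilation start to infusion: 24 or 48

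Formulas, with both groups followed to day 30 from ventilation:

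- Risk of failing before infusion: q = p × f × T/48
- Control risk: p
- Siltuximab risk: (p − q)/(1 − q)
- Spurious odds ratio: (p − q)/p = 1 − f × T/48

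| p | f | T (h) | q | Siltuximab risk | Spurious difference (points) | Odds ratio |
|---|---|---|---|---|---|---|
| 0.30 | 0.10 | 24 | 0.015 | 0.285/0.985 = 28.9% | 1.1 | 0.95 |
| 0.50 | 0.30 | 24 | 0.075 | 0.425/0.925 = 45.9% | 4.1 | 0.85 |
| 0.50 | 0.40 | 24 | 0.100 | 0.400/0.900 = 44.4% | 5.6 | 0.80 |
| 0.30 | 0.10 | 48 | 0.030 | 0.270/0.970 = 27.8% | 2.2 | 0.90 |
| 0.50 | 0.30 | 48 | 0.150 | 0.350/0.850 = 41.2% | 8.8 | 0.70 |
| 0.60 | 0.40 | 48 | 0.240 | 0.360/0.760 = 47.4% | 12.6 | 0.60 |

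Infusion times uniform over 0 to 48 hours give the 24-hour results. In about 19 Cohort A patients per group, 1.1 to 5.6 points is 0.2 to 1.1 fewer siltuximab failures, and 12.6 points is 2.4 fewer. In about 6 Cohort B patients, 5.6 points is 6 × 0.056 = 0.3 of a patient.

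**Day counts.** Deaths or weaning before infusion remove short stays from the siltuximab group only, which lengthens its average ICU stay and works against the drug. Removing patients intubated before infusion takes invasive-ventilation days out of siltuximab Cohort A, which works for it. The net direction is not determined.

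**After alignment.** If the control is also at risk at T and both are followed from T, both risks are (p − q)/(1 − q): difference 0, odds ratio 1.00.

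**The case against.** **The study is exploratory and makes no formal comparison.** True (8.2, 11.2 and 11.2.3), and this limits the consequences. It does not remove the bias, which sits in the descriptive rates.

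**Control time zero is not stated.** Correct. Section 10.1.1 sets a recording window, not an endpoint origin, and the start for controls is inferred from it. Criteria 4 and 5 speak of subjects generally and may also cover controls. But being treated is not defined for a control, and the start of some other therapy would not be aligned to the partner's infusion.

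**Consent may screen out early control failures.** Possibly some. The doctor's emergency consent (10.1.2) and the provision for deceased patients (9.1.1) weaken that filter, and it is not a designed safeguard.

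**The SAP may settle it.** Definitions of baseline and study days can be left there and are not pressed here. Who may be chosen as a control is a design matter that the protocol itself sets out.

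**Stronger readings a reader might infer, which the documents do not support:**

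- *All early failures fall among controls.* Only those before infusion are excluded from the siltuximab group.
- *Both primary endpoints favour siltuximab throughout.* Cohort B's also contains ICU stay, where the distortion can run against the drug.
- *A false relative reduction of 28%.* With a 40% control risk and infusion uniform over 48 hours, 11.4 points (11.4/40 = 28%) does come out of a Weibull model with shape 0.3. That model puts 51% of control events in the first 48 hours and about 17% in the first hour, and nothing in the protocol suggests this. A constant hazard gives 1.0 point.

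**Conclusion.** The concern holds in this form: control selection is not aligned to infusion time, so the rate of intubation or death in Cohort A and 30-day mortality in Cohort B are biased towards siltuximab under no drug effect. ICU stay and other day counts can be distorted in either direction.

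The direction on the event endpoints follows from the design if controls are counted from first ventilation, which is the only start the protocol gives. The size rests on assumed risks and timings: about 1 to 6 points with infusion at 24 hours on average, 2.2 to 12.6 points if all infusions were at 48 hours, and less if they were early. This should be fixed before controls are selected. It is not graver than that, because the study is descriptive, makes no formal claim, and in most scenarios the shift is about one patient or less per cohort.

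**What to change.** Add to the Match Criteria in section 8.1 and the Synopsis:

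- The index time of a siltuximab patient is the infusion.
- The matched control receives an index time at the same number of hours after the start of the same support (NIV/CPAP in Cohort A, invasive ventilation in Cohort B), within a stated tolerance.
- At that time the control must be alive, still on that support, not intubated (Cohort A), and in the same P/F class.
- All endpoints, including P/F at days 3, 8 and 15, are counted from the index time in both groups, and data are collected to 30 days after it.

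**Cost:** protocol wording, one derived time per control, and up to two more days of chart data per patient. Candidate controls who failed or were weaned before the index time are lost. Under the assumptions above, the loss to failure alone is q, from 0.30 × 0.10 × 0.5 = 1.5% to 0.60 × 0.40 × 0.5 = 12% of candidates at 24 hours. Weaning adds to this by an amount the protocol does not allow one to estimate. At a single site with four match factors already in use, the tolerance should be set with the available pool in mind.

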 - o Hospital admission date;
 - ICU admission (if applicable);
 - Mobility;
 - o Respiratory parameters;
 - o Use of inotropic medication;
 - o RR/MAP;
 - Diagnostic interventions (X-ray of thorax, computerized tomography [CT] scans);
 - o Symptoms (fever, rash, abnormal cardiac function);
 - o Mechanical ventilation;
 - o Extracorporeal membrane oxygenation (ECMO).
- Infectious Disease Parameters:
 - Inflammatory markers;
 - Peripheral edema;
 - O Cytokine panel (full work-up pre- and post-treatment [serum]);
 - o Pre-treatment C-reactive protein (CRP) levels;
 - o Post-treatment CRP levels/24 h
 - Cardiac parameters/oxygen saturation;
- General Disease Parameters:
 - APACHE II score;
 - Performance status (Eastern Cooperative Oncology Group [ECOG]/Karnofsky);
 - o Laboratory assessments;
 - Virus titer;
 - o IL-6 status: pre-treatment serum IL-6 levels (ELISA or similar approach, e.g. multiplex cytokine array);
 - Extended blood panel (hemoglobin/hematocrit [Hb/Ht]), thrombocytes (including peripheral blood mononuclear cell [PMBC]);
 - Coagulation status;
 - o History of Human Immunodeficiency virus (HIV), Human herpes virus (HHV-8), hepatitis and tuberculosis infection.

	-
Inclusion Criteria	Patients must meet the following criteria to be eligible to participate in the study:
	1. Clinical and radiological diagnosis of pulmonary infection by COVID-19
	2. Positive microbiological evidence of SARS-CoV-2 infection
	3. Diagnosis of acute respiratory distress syndrome clinical panel in accordance with Berlin 2012 criteria
	4. For Cohort A only: subjects are eligible if they are enrolled and treated within 48 hours from the beginning of NIV or CPAP
	5. For Cohort B only: subjects are eligible if they are enrolled and treated within 48 hours from the beginning of invasive ventilation
Exclusion Criteria	Patients who meet the following criteria may NOT participate in the study.
	1. Active infection of bacterial or viral (non COVID-19) origin
Number of Patients	Up to 50 patients: 50% receiving treatment (Cohort A and Cohort B) and 50% matched case controls.
Countries/Number of Sites	1 site in Italy
Statistical Methods	All data will be summarized using descriptive statistical analyses as appropriate.
	All data will be presented in by-subject data listings.

PROTOCOL APPROVED BY PRINCIPAL INVESTIGATOR

Name / Title: [name] PhD

Address: [name]
Contact Info: UOC Ematologia

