6 STUDY OBJECTIVES

The is a case control study to observe treatment and collect data on two cohorts of patients treated with siltuximab and a corresponding case control group of patients who have developed severe respiratory complications with COVID-19 infection.

Primary objective

Cohort A: reduction of the need of invasive ventilation or 30-day mortality

Cohort B: reduction of mortality

Secondary objectives

Cohort A

Reduction of the need of time of ventilatory support

Improvement of the lung function

Improvement of radiologic findings

Cohort B

Reduction of days of need of intubation

Percentage of patients that undergo to tracheostomy

Improvement of the lung function

Improvement of radiologic findings

Primary endpoint:

Cohort A: Reduction of the rate of need of invasive ventilation or 30-day mortality

Cohort B: Reduction of length of ICU staying or 30-day mortality

Secondary endpoints:

Cohort A

Reduction of days of need of ventilatory support

Improvement of P/F fraction (resolution of ARDS i.e. P/F>300, or increase from baseline value of at least 50% if P/F>100 or 100% if P/F<100, at day 3, 8 and 15)

Reduction of the duration of invasive ventilation or length of ICU

Improvement of radiologic imaging

Cohort B

Reduction of days of need of intubation

Percentage of patients that undergo to tracheostomy

Improvement of P/F fraction (resolution of ARDS i.e. P/F>300, or increase from baseline value of at least 50% if P/F >100 or 100% if P/F<100, at day 3, 8 and 15)

Improvement of radiologic imaging

Exploratory end points

Correlation of outcomes with IL-6 levels

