11.1 Sample Size Determination

No statistical sample size estimation was performed. For this study patients from one single center in Italy will be enrolled as follows:

- All patients treated with siltuximab diagnosed with COVID-19 infection who have developed serious respiratory complications, and
- An equal number of case control patients that consented to their data collection.

It is estimated that in total up to 50 patients will be enrolled.

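### Control status has no index time, so a Cohort A control who is intubated and then given siltuximab can move to treated Cohort B and be lost as a control failure

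*Protocol*

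**What the plan says.** Protocol section 8.1 describes a single-centre study with retrospective data collection, run while the compassionate use programme is still enrolling. Its definition of a control is "Each patient will be matched to a consented case control receiving treatment other than siltuximab for their condition". "Patients receiving siltuximab and controls will be matched according to the following criteria": age by decade, sex, baseline P/F band and antiviral therapy. Time since the start of ventilatory support is not among them.

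Four other statements bear on who can be a control:

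- Section 6 gives the first primary endpoint as "Cohort A: Reduction of the rate of need of invasive ventilation or 30-day mortality".
- Section 9.1.1, criterion 4: "For Cohort A only: subjects are eligible if they are enrolled and treated within 48 hours from the beginning of NIV or CPAP".
- Section 9.1.1, criterion 5: "For Cohort B only: subjects are eligible if they are enrolled and treated within 48 hours from the beginning of invasive ventilation".
- Section 11.1 enrols "All patients treated with siltuximab diagnosed with COVID-19 infection who have developed serious respiratory complications, and" an equal number of consenting controls. The synopsis gives the total as "Up to 50 patients: 50% receiving treatment (Cohort A and Cohort B) and 50% matched case controls", so treated and control patients are described as separate halves.

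The protocol gives no time zero for controls. It has no rule for a patient who starts siltuximab after qualifying as a control.

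**The concern.** The event that makes a Cohort A patient a failure is the same event that makes a patient eligible for siltuximab under Cohort B. Controls are chosen retrospectively, so later treatment is already known when they are picked. If control status is judged over the whole stay, membership of the Cohort A control group can depend on treatment that followed the outcome.

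The loss is one-sided. An untreated patient on CPAP who recovers stays eligible as a control. One who is intubated and then given siltuximab does not. On the treated side, a Cohort A patient who is intubated after siltuximab still counts as a failure. If the site instead keeps the crossover patient as a control, part of that patient's 30-day mortality follow-up comes after siltuximab, and the protocol does not say how to report it. Two sites or two analysts could follow section 8.1 faithfully and form different control groups.

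**Working it through.** **Inputs from the protocol.** Up to 50 patients, half treated: 50 × 0.5 = 25. Section 8.1 gives the cohorts as "split in an approximate 3:1 ratio: 75% will be in Cohort A and are not in an ICU setting". Hence 25 × 0.75 = 18.75 (about 19) in Cohort A and 25 × 0.25 = 6.25 (about 6) in Cohort B, with about 19 Cohort A controls. The protocol states no event rate, power or sample size calculation, so it has no figure of its own to reproduce.

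**Assumptions, not in the protocol.** The true event rate among untreated NIV/CPAP patients is p = 0.40. The number of untreated NIV/CPAP patients from whom controls are drawn is M. The number of those who are intubated, then given siltuximab and so lost as controls is c. Each crossover becomes a treated Cohort B patient, so c is at most about 6.

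**Formula.** Every lost patient is a failure, so the apparent control rate is (Mp − c)/(M − c).

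| Pool M | c = 6 | c = 1 |
|---|---|---|
| 40 | (16 − 6)/34 = 29.4% | 15/39 = 38.5% |
| 100 | (40 − 6)/94 = 36.2% | 39/99 = 39.4% |
| 300 | (120 − 6)/294 = 38.8% | 119/299 = 39.8% |

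For c = 6 the falls from 40% are 10.6, 3.8 and 1.2 points.

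**Sensitivity to p (c = 6).** At p = 0.30 the fall is 9.5 points for M = 50, 4.5 for M = 100 and 1.4 for M = 300. At p = 0.50 it is 6.8, 3.2 and 1.0 points. The direction is the same for any c above zero.

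**What the 29% figure needs.** If 30% of the pool is intubated (a further assumption) and half of those cross over, 15% of the pool is lost: (0.40 − 0.15)/(1 − 0.15) = 29.4%. With at most 6 crossovers, that requires a pool of no more than 6/0.15 = 40 patients, with every Cohort B patient a crossover.

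**Scale.** Among 19 controls, 40% is 19 × 0.40 = 7.6 expected events. The c = 6 rates above give 5.6, 6.9 and 7.4 events for M = 40, 100 and 300. The standard error of a difference between two groups of 19 at p = 0.40 is √(2 × 0.40 × 0.60/19) = 0.159, about 16 points.

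**An effect in the other direction.** A treated Cohort A patient must be free of invasive ventilation until the infusion, which may come up to 48 hours after NIV or CPAP starts. Controls have no matching requirement. If their follow-up begins at the start of NIV or CPAP, they can fail in an interval in which treated patients by definition cannot. That raises the control rate relative to the treated rate. The protocol gives nothing from which to size it.

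**The case against.** The strongest reply is that section 8.1 can be read as assigning control status early. Section 9.1.1 applies its criteria to all participants, criterion 4 sets a 48-hour limit, and P/F is matched at baseline. The definition also describes what a control is receiving and does not require that siltuximab was never received. On that reading, a patient intubated on day 4 would already be a control and would stay one. This reading is possible, but the protocol does not state it. It also leaves open what happens when such a patient, under section 11.1, counts among all those treated.

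Other parts of the reply stand. No section says that any Cohort B patient was first left untreated on NIV or CPAP, and the compassionate use protocol that might settle this is not at hand. If there were no crossovers, this bias is zero. Deaths without intubation are unaffected. Later siltuximab would not be invisible, because section 10.1.7 collects treatment start and stop dates and section 11.2 requires by-subject listings.

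A reader might infer three stronger conclusions that the documents do not support:

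- **That 6 of about 19 control failures could vanish.** Losses act on the whole untreated pool from which the 19 are drawn, not on the 19 themselves.
- **That siltuximab is made to look worse overall.** This mechanism works against siltuximab, but the unmatched time on ventilation may work in its favour.
- **That the Cohort A primary objective cannot be answered.** Section 8.2 presents the study as hypothesis-generating. Section 11 plans a descriptive comparison, and section 11.2.3 rules out statistical comparisons between the groups. The harm is a possibly distorted descriptive estimate, not a false test result.

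**Conclusion.** The gap is real and worth closing. The control definition has no index time, and the text as written lets siltuximab given after the Cohort A event decide who remains a Cohort A control. Any crossover of this kind lowers the Cohort A control event rate.

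The size cannot be fixed from the protocol. It rests on an assumed event rate, an unstated pool and an unknown number of crossovers, bounded at about 6. For pools of 100 or more it is a few points at most, well inside the imprecision of 19 against 19. It becomes large only if the pool is about 40 or fewer and nearly all Cohort B patients crossed over. The net direction is uncertain.

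The issue is one of design and not only of analysis, because a later plan cannot recover controls who were never selected. Section 8.2 says the control group is there to allow direct comparison, so a descriptive analysis does not make the selection rule unimportant.

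**What to change.** Add one paragraph to section 8.1 stating that:

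- control status is fixed at an index time comparable to the matched treated patient's time of siltuximab, measured from the start of NIV or CPAP in Cohort A and from the start of invasive ventilation in Cohort B (a window within the existing 48-hour limit is enough; an exact hour match is not needed);
- the control must be event-free and siltuximab-free at that time;
- siltuximab given later does not remove the patient from the control group;
- intubation counts as a Cohort A event when it occurs.

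Flag later siltuximab from the dates already collected under section 10.1.7. Report how many controls received it, and how many patients serve both as a Cohort A control and as a treated Cohort B patient. Do not add a mortality summary censored at the start of siltuximab. These patients have just been intubated, so that censoring would be informative.

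Under this rule, later crossovers stay in the pool as failures. In the example above the control rate returns to 40%, and the matched index time also addresses the opposing effect.

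The cost is one paragraph and one derived flag, with no new data. A few patients may appear in two roles, some control deaths will follow siltuximab, and matching becomes slightly harder.
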